6.2.3.1 Model checking procedures

[figure not shown]
The model assumption of no first-order carry-over effect and negative binomial distribution will be examined for three-day total number of stools with a BSC score of 6 or 7 per period and three-day total number of bowel movements per period similarly to the primary endpoint. Missing data will be assumed to be missing at random and thus the above analyses will be performed on all available data. There will be no imputation of missing data.

6.2.3.2 Graphical presentation of results

Least-square mean and least-square mean difference between treatment groups with 80% confidence intervals will be plotted for all secondary endpoints by treatment.

7 Statistical methods for safety and tolerability data

7.1 Variables

Adverse events, vital signs (blood pressure, pulse rate, body temperature), ECG intervals, laboratory measurements, as well as subject demographics, baseline characteristics, and treatment information.

7.2 Descriptive analyses

Subject demographics and other baseline characteristics

All data for background and demographic variables will be listed by treatment sequence and subjects in the safety analysis set. Summary statistics will be provided for all subjects in the safety analysis dataset, as well as for each treatment sequence.

Relevant medical history, current medical conditions, results of laboratory screens, drug tests and any other relevant information will be listed by treatment sequence and subject.

Subject disposition (frequency of completion/discontinuation and reasons for early discontinuation) will be summarized by epoch and treatment sequence.

Treatment

Data for study drug administration and meal/supplement dosing and concomitant therapies will be listed by treatment sequence and subject. Number of dose administration will be summarized by treatment.

Vital signs

All vital signs data will be listed by treatment sequence, subject, and visit/time and if ranges are available abnormalities (and relevant orthostatic changes) will be flagged. Summary statistics will be provided by treatment and visit/time.

ECG evaluations

All ECG data will be listed by treatment, subject and visit/time, abnormalities will be flagged. Summary statistics will be provided by treatment and visit/time.

Clinical laboratory evaluations

All laboratory data will be listed by treatment, subject, and visit/time and if normal ranges are available abnormalities will be flagged. A separate listing is provided presenting all parameters in a subject with any abnormal values. Summary statistics will be provided by treatment and visit/time.

Adverse events (AEs)

All information obtained on adverse events will be listed by treatment sequence and subject.

The number and percentage of subjects with adverse events will be tabulated by body system and preferred term with a breakdown by treatment. An adverse event starting in one period/epoch and continuing into the next period/epoch is counted only in the onset period. A subject with multiple adverse events within a body system and treatment period/epoch is only counted once towards the total of this body system and treatment. If AE dates are needed to assign onset period and the dates are missing, AE date will be imputed by the following rule: if year is missing there will be no imputation of date. Otherwise missing month will be imputed by January, and missing day will be imputed by 1st.

Serious adverse events and adverse events leading to early discontinuation will be listed by treatment sequence and subject.

Adverse events leading to death will be listed by treatment sequence and subject.

For the legal requirements of ClinicalTrials.gov and EudraCT, two required tables on on-treatment/treatment emergent adverse events which are not serious adverse events with an incidence greater than 1% and on on-treatment/treatment emergent serious adverse events and SAE suspected to be related to study treatment will be provided by system organ class and preferred term on the safety set population.

If for a same patient, several consecutive AEs (irrespective of study treatment causality, seriousness and severity) occurred with the same SOC and PT:

- a single occurrence will be counted if there is ≤ 1 day gap between the end date of the preceding AE and the start date of the consecutive AE
- more than one occurrence will be counted if there is > 1 day gap between the end date of the preceding AE and the start date of the consecutive AE.

For occurrence, the presence of at least one SAE / SAE suspected to be related to study treatment / non SAE has to be checked in a block e.g., among AE's in a ≤ 1 day gap block, if at least one SAE is occurring, then one occurrence is calculated for that SAE.

[figure not shown]
The number of deaths resulting from SAEs suspected to be related to study treatment and SAEs irrespective of study treatment relationship will be provided by SOC and PT.

[figure not shown]
Immunogenicity

Not applicable

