All other samples and measurements will be taken according to the [Assessment schedule](#).

Part A: Effects of Carbohydrate in the Breakfast Meals

Treatment Period I (Day 1 to Day 3); Period II (Day 9 to Day 11); Period III (Day 17 to Day 19)

Starting on the morning of Day 1 and through Day 3 of each treatment period, each subject will receive LIK066 50 mg qd in the morning immediately before the assigned breakfast meal according to their assigned treatment sequence. All subjects will take 50 mg LIK066 once daily with their assigned breakfast meal containing either 50% carbohydrate, 25% carbohydrate, or no carbohydrate. For lunch and dinner, menu options will be offered so that the participants can follow their usual dietary habits. These menus will be designed in accordance with the current Recommended Dietary Guidelines ([United States Department of Agriculture 2015](#)). The estimated calories consumed will be documented for each meal and for each subject. As with the baseline period, 24-hr stool collection will be done and stool assessment will be recorded for every bowel movement of every subject according to the [Assessment schedule](#).

[REDACTED]

Twenty-four (24) hour stool samples will be collected from Day 3 to Day 4 morning (approximately 07.00 to 07.00) of each treatment period for various assessments of fecal parameters according to the [Assessment schedule](#).

[REDACTED] various assessments including UGE24 and electrolytes according to the [Assessment schedule](#).

[REDACTED] At approximately 07.30, a 600 calorie standardized breakfast meal containing either 50% or 25% or 0% carbohydrate as designated will be served, and LIK066 50 mg will be administered immediately before the breakfast meal. Each subject will consume the designated breakfast within 15 mins.

[REDACTED]
[REDACTED]
Lunch will be served at approximately 13:00 (after completion of the PD sample collection and at least 5 hours from breakfast), and dinner will be served at approximately 18.30. The timing of meals should be harmonized on all days (Day -1, Day 3, Day 11, and Day 19) when PD are measured to minimize the effects of diurnal rhythm.

All other measurements and blood samples will be taken according to the [Assessment schedule](#).

Washout Period I (Day 4 to Day 8); Period II (Day 12 to Day 16); Period III (Day 20 to Day 22)

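### The AE partial-date rule (1st of month, January) is meant to assign the onset period but cannot resolve 8-day periods; it misplaces about 86% of post-dose onsets with a missing day, though few AEs should need it

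*SAP*

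**What the plan says.** SAP 7.2 (Adverse events) tabulates AEs by body system and preferred term, broken down by treatment. The link from event to treatment is the onset period: "An adverse event starting in one period/epoch and continuing into the next period/epoch is counted only in the onset period". For incomplete dates the SAP says "If AE dates are needed to assign onset period and the dates are missing, AE date will be imputed by the following rule": with an unknown year, "if year is missing there will be no imputation of date"; and then "Otherwise missing month will be imputed by January, and missing day will be imputed by 1st".

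The AE text shown sets no lower limit at first dose or consent. It makes no use of the visit, the epoch of report or the AE end date.

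Protocol 3.1 gives the calendar. Dosing is on Days 1-3, 9-11 and 17-19, with washout on Days 4-8, 12-16 and 20-22. The assessment schedule (Protocol Table 8-1) places each washout inside the preceding treatment period. The periods are therefore Days 1-8, 9-16 and 17-22. Protocol 9.1 collects AEs from consent to the end-of-study visit, with start and end dates.

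**The concern.** The rule's stated job is to pick one of three consecutive periods lasting 8, 8 and 6 days. Moving a date to the 1st of its month can shift it by up to 30 days, and moving it to January by far more. The imputed date can never be later than the true one, so the error runs in one direction only.

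A displaced post-dose event has two possible destinations. It may land before first dose and drop out of the by-treatment counts. Or it may land in an earlier period and be credited to a different breakfast or supplement, which is the comparison the crossover makes. For tolerability data, losing on-treatment events is the non-conservative direction.

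**Working it through.** The documents give no figure for misplaced AE dates, so there is none to reproduce. The check applies the rule to every possible case.

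**Inputs from the documents:** the rule (SAP 7.2); periods on Days 1-8, 9-16 and 17-22 (Protocol 3.1 and Table 8-1).

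**Assumptions:** first-dose dates uniform over the 365 days of 2017; true onset uniform over Days 1-22; where the month is missing, the day is missing too.

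**Two examples (missing day).**
- First dose 10 July: Days 1-22 are 10-31 July. Every onset becomes 1 July, so all 22 onset days move before first dose.
- First dose 25 July: 1 August is Day 8, in Period 1. Onsets on 25-31 July (7 days) become 1 July, before first dose. All 14 onset days of Periods 2 and 3 become Day 8 and are credited to Period 1's treatment. Only an onset on 1 August is right, so 21/22 = 95% are wrong.

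**Closed form (missing day).** An average month has 365/12 = 30.4 days. An onset on the j-th day of its period stays in that period only if its day of the month is at most j, which has probability j/30.4. The mean of j is 4.5 in an 8-day period and 3.5 in a 6-day period.
- Right: (8×4.5 + 8×4.5 + 6×3.5)/22/30.4 = 13.9%. Wrong: 86.1%.
- Before first dose: an onset on Day k moves pre-dose if its day of the month exceeds k. The mean of k over 1-22 is 11.5, so 1 − 11.5/30.4 = 62.2%.
- In an earlier treatment period: 86.1 − 62.2 = 23.9%.

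Full enumeration of 365 start dates × 22 onset days gives the same 86.1%, 62.2% and 23.9%.

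**By true period (missing day):**

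| True period | Wrong | Before first dose | Earlier treatment period |
|---|---|---|---|
| 1 | 85.2% | 85.2% | 0% |
| 2 | 85.2% | 58.9% | 26.3% |
| 3 | 88.5% | 35.9% | 52.6% |

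**Sensitivity (missing day, wrong period):**
- onset on Days 1-19 only: 86.5%
- onset on dosing days only: 93.4%
- treatment and washout counted as separate epochs: 91.9%
- first doses restricted to 21 June-27 September 2017 (the dates of the first SAP version and of v02; enrolment dates are not given): 85.8%, with 60.3% before first dose

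**Month also missing:** 98.8% wrong for starts over the year; 100% wrong, all pre-dose, for the June-September window.

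**Pre-dose AEs included (missing day).** A true pre-dose onset is always left pre-dose, so the rule is right for it and only the denominator changes.
- Onset Day -3 to 22 (25 days): 22/25 × 86.1% = 75.8%
- Onset Day -28 to 22 (50 days): 22/50 × 86.1% = 37.9%

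**The case against.** The strongest reply is that the rule will hardly ever be used. It is a fallback, applied only "If AE dates are needed to assign onset period and the dates are missing". Subjects are domiciled for about 25 days, staff give every dose, start and end dates are required for each AE, safety data are source-verified, and discrepancies are queried before lock. A missing month in a resident subject is scarcely plausible. This stands, and it is why the point is minor.

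The headline percentage is also conditional. A reader might infer that 86% of all partial AE dates go astray. The documents do not support that: AEs are collected from consent, and the rule handles screening and run-in events correctly.

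A reader might also infer that the tolerability conclusion is at risk. It is not. The primary and main secondary variables are stool counts (SAP 6.1.1 and 6.2.1), which use no AE dates. The AE tables are descriptive in a non-confirmatory study, and every AE is still listed by sequence and subject. Nor is there an inherent bias for or against one diet or supplement, because within each part every treatment appears once in each period position.

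Finally, a reader might assume that the treatment-emergent tables for the registries are distorted too. SAP 7.2 does not say how treatment-emergent status is determined or whether the imputed date feeds it, so that is possible but not shown.

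None of this rescues the rule where it applies: a post-dose AE with a partial date is usually put in the wrong period.

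**Conclusion.** The point holds as a minor defect. This is a stated rule that fails at its stated purpose, not merely missing detail. For true onset on Days 1-22, a missing day gives the wrong period in about 86% of cases (62% before first dose, 24% in an earlier period), and a missing day and month in about 99-100%. Over wider onset windows that include pre-dose AEs, the missing-day error is 76% (from Day -3) or 38% (from Day -28).

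The percentages rest on uniform onset and uniform first-dose dates. The direction does not: an imputed date is never later than the true one. The number of AEs affected cannot be derived from the documents and should be small.

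**What to change.** For partial onset dates, replace the 1st/January rule in SAP 7.2 as follows.
- Assign the period from the visit or epoch in which the AE was first recorded, checked against the known date parts and the AE end date.
- If more than one period remains possible, tabulate the AE in a separate row as on study, period unknown. Count it as treatment-emergent unless the record shows pre-dose onset, and do not assign it to one treatment.

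The simpler remedy of taking the earliest period compatible with the known date parts, never before first dose, is not recommended. In the same missing-day enumeration it is right for only 45% of onsets on Days 1-22 and puts 84% of them in Period 1. For onset Day -28 to 22, without other evidence of pre-dose onset, it is right in 46%, against 62% (100 − 37.9) for the present rule. Adding the AE end date would not help it, because an upper bound cannot change the earliest compatible period.

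Cost: a few sentences in the SAP, a little programming, possibly one extra row in the AE table, and an occasional pre-dose AE counted as treatment-emergent. The documents do not say whether the CRF holds the visit of first record for each AE. If it does not, the site's source notes would have to supply it for the few events concerned.
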